9.8.1 HCV RNA Sample

HCV RNA sample – the following needs to be documented:

- **Quantitative** HCV RNA by PCR test
 - Test name and result **in IU/mL**
 - Lower limit of detection (LLoD) **in IU/mL** and lower limit of quantification (LLoQ) **in IU/mL**
- **Qualitative** HCV RNA by PCR test
 - Test name and result (**positive/negative**)
 - LLoD **in IU/mL**

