9.9 Variables

9.9.1 Primary Variable

- The percentage of patients achieving SVR12 (undetectable viral load at 12 week after the last actual dose of the ABBVIE 3D REGIMEN)

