9.13.3 Effectiveness Analysis

The primary effectiveness analysis on clinical outcomes will be performed on all patients in the CP stratified by the CP analysis groups. Due to the non-interventional nature of this study several different methods for determination of the HCV RNA value can be applied. For the purpose of the statistical analysis, a HCV RNA measurement is considered ≤ 50 IU/mL,

- if a PCR test was used
- and the test result is undetectable and the LLoD of the test is ≤ 50 IU/mL or the test result is unquantifiable and the LLoQ is ≤ 50 IU/mL

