Data MATRIX

SF_STAT001_ver 2_Eng
Approval Date 18 July 2017

PI6-253 (CITRIN) _ STATISTICAL ANALYSIS PLAN _ FINAL 2.0 _ 16 Mar 2018

Protocol Number: PI6-253 (CITRIN)

Protocol Title: Real world evidence study of the effectiveness of Paritaprevir/r –
Ombitasvir + Dasabuvir without Ribavirin in patients with chronic HCV
G1b infection and compensated liver cirrhosis in the Russian Federation
– an observational, multi-center study

SAP version: Final 2.0

Effective date: 19 Mar 2018

REVISION HISTORY

| Nº | Version | Date | Changes |
|----|---------|------------|---|
| 1 | 1.0 | 16.08.2017 | New Document 
1) section 9 and corresponding tables shells was updated.– additionally to efficiency endpoints the following virologic outcomes were added to the analysis: breakthrough, failure to suppress and premature study drug discontinuation with no on-treatment virologic failure;– due to the fact that in the Russian clinical practice tests for HCV RNA often have limit of detection higher than 50 IU/mL and may vary across laboratories, the definitions for effectiveness outcomes were adjusted;– additional frequency tables for patients in subgroup without missing SVR12 data category were added;– method of 95% confidence interval calculation for odds ratio in logistic regression analysis was specified; |
| 2 | 2.0 | 16.03.2018 | 
2) the information about time windows for clinical laboratory data was moved to section 4.1 “General study design and plan”;3) tables shells for demographics and baseline characteristics was changed: one table was divided into several tables;4) list of tables, figures and listings was added. |

P16-253 (CITRIN) _ STATISTICAL ANALYSIS PLAN _ FINAL 2.0 _ 16 Mar 2018

TABLE OF CONTENTS

| | | |
|------|--|------------------------------|
| 1 | Abbreviations and definitions | 4 |
| 2 | Introduction | 5 |
| 3 | Study objectives and variables | 5 |
| 3.1 | Study objectives | 5 |
| 3.2 | Variables | 6 |
| 4 | Study design | 6 |
| 4.1 | General study design and plan | 6 |
| 4.2 | Sample size | 7 |
| 4.3 | Randomization and blinding | 8 |
| 4.4 | Planned analyses | 7 |
| 5 | General considerations | 8 |
| 5.1 | Reference start date/time, study day, baseline | Error! Bookmark not defined. |
| 5.2 | Windowing conventions | Error! Bookmark not defined. |
| 6 | Analysis populations | 8 |
| 7 | Statistical considerations | 9 |
| 7.1 | Standard descriptive statistics | 9 |

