8.5 Prior and concurrent medications

All medications will be coded using WHODD version Jun 2015 (or actual version on the time of the study completion) according Data MATRIX LLC SOP [3]. Prior and concurrent medications will be presented in a separate listings and tables.

Prior medication will be determined using “MOST RECENT PRIOR THERAPY FOR CHC” flag in the CMCAT variable of CM domain of the database. Concurrent medications will be determined using “CO-MEDICATION” flag in the CMCAT variable of CM domain of the database.

Additionally listings will contain the following information for prior CHC therapy:

- presence of prior treatment for CHC;
- generic drug name;
- initial dose (by generic drug name groups and units groups);
- start frequency (by generic drug name groups);
- duration (by generic drug name groups, in weeks);
- outcome prior treatment.

9 Effectiveness analysis

All analyses of effectiveness will be performed on the TP, CP and CPSFU populations with separate tables for each population as the result. Tables for equal sets (contain exactly the

P16-253 (CITRIN) _ STATISTICAL ANALYSIS PLAN _ FINAL 2.0 _ 16 Mar 2018

same patients) will not be presented, equal sets will be pointed in the footnote with description only.

The following effectiveness outcomes will be included in the analyses:

- SVR12 achieving;
- virological response at EoT;
- patients with at least one and each of SVR12 non-response categories:
 - relapse during treatment phase;
 - relapse after EoT;
 - failure to suppress;
 - premature study drug discontinuation with no on-treatment virologic failure;
 - missing SVR12 data.

Due to the fact that in the Russian clinical practice tests for HCV RNA often have limit of detection higher than 50 IU/mL and may vary across laboratories, effectiveness outcomes will be analyzed with the following definitions:

- SVR12 achieving (single last HCV RNA value <50 IU/mL or undetectable/negative 12 weeks after the last actual dose of the ABBVIE REGIMEN);
- virological response (HCV RNA <50 IU/mL or undetectable/negative) at EoT;
- patients with at least one and each of SVR12 non-response categories:
 - relapse during treatment phase (breakthrough, i.e. at least one documented HCV RNA value <50 IU/mL or undetectable/negative followed by HCV RNA value \geq 50 IU/mL or positive during treatment);

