Table 1.13.3 Concurrent Medications for CHC (treatment-experienced groups)
Table 1.13.4 Concurrent Medications for CHC (Child Pugh score groups)

for the target and safety populations

Table 1.13.5 Concurrent Medications for CHC
Table 1.13.6 Concurrent Medications for CHC

P16-253 (CITRIN) _ STATISTICAL ANALYSIS PLAN _ FINAL 2.0 _ 16 Mar 2018
Effectiveness Analyses (TP)

 AbbVie Ltd
 P16-253

Table 2.1.1.1 Percentage for effectiveness endpoints

The target population (TP)

Page X of X

| Parameter Statistics | Total (N=XX) |
|---|------------------------------|
| | n (%) |
| | [95% CI] |
| SVR12 achieving (single last HCV RNA value <50 IU/mL 12 weeks after the last actual dose of the ABBVIE REGIMEN) | XX (XX.X) [XX.XX - XX.XX] |
| SVR12 non-response | XX (XX.X) [XX.XX - XX.XX] |
| Patients with breakthrough (at least one documented HCV RNA value <50 IU/mL followed by HCV RNA ≥50 IU/mL during treatment) | XX (XX.X) [XX.XX - XX.XX] |
| Failure to suppress (each measured on-treatment HCV RNA value ≥50 IU/mL) | XX (XX.X) [XX.XX - XX.XX] |
| Patients with relapse (HCV RNA value <50 IU/mL at EoT or at the last on-treatment HCV RNA measurement followed by HCV RNA ≥50 IU/mL post-treatment) | XX (XX.X) [XX.XX - XX.XX] |
| Patients with premature study drug discontinuation with no on-treatment virological failure (breakthrough or failure to suppress) | XX (XX.X) [XX.XX - XX.XX] |
| Patients with missing SVR12 data | XX (XX.X) [XX.XX - XX.XX] |
| Patients with virological response (HCV RNA <50 IU/mL) at EoT | XX (XX.X) [XX.XX - XX.XX] |

N: the number of subjects in the target population. n: number of subjects within a specific category. Percentages are calculated as 100 x (n/N).
 EoT: end of treatment. SVR12: sustained virological response at 12 weeks after EoT. 95% CI: 95% confidence interval (the Clopper-Pearson method).

Program code, date, time

Data extracted: DD.MM.YYYY

P16-253 (CITRIN) _ STATISTICAL ANALYSIS PLAN _ FINAL 2.0 _ 16 Mar 2018

 AbbVie Ltd
 P16-253

Table 2.1.2.1 Percentage for effectiveness endpoints without patients with missing SVR12 results
 The target population (TP)
 Page X of X

| Parameter Statistics | Total (N=XX) n (%) [95% CI] |
|---|--------------------------------------|
| SVR12 achieving (single last HCV RNA value <50 IU/mL 12 weeks after the last actual dose of the ABBVIE REGIMEN) | XX (XX.X) [XX.XX - XX.XX] |
| SVR12 non-response | XX (XX.X) [XX.XX - XX.XX] |

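### SAP section 9 counts any negative HCV RNA result as SVR12 or EoT response whatever the test's detection limit, while the shells keep a 50 IU/mL label and no table uses the protocol 9.13.3 rule

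*SAP*

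**What the plan says.** **Protocol.** Section 9.13.3 sets the rule for the statistical analysis. A PCR result is taken as at or below 50 IU/mL if the test was PCR "and the test result is undetectable and the LLoD of the test is" at most 50 IU/mL, "or the test result is unquantifiable and the LLoQ is" at most 50. The imputation rules in 9.13.1 repeat both limits. Section 9.13.4 defines SVR12 as a last value below 50 IU/mL at least 84 days after the last dose. Section 9.9.1 is looser and asks only for "undetectable viral load at 12 week after the last actual dose of the ABBVIE 3D REGIMEN". Section 9.8.1 asks sites to record the LLoD for every test and the lower limit of quantification (LLoQ) for quantitative tests. It accepts qualitative tests reported as positive or negative.

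**SAP.** Section 9 notes that "in the Russian clinical practice tests for HCV RNA often have limit of detection higher than 50 IU/mL". It then counts as SVR12 a last value below 50 IU/mL "or undetectable/negative 12 weeks after the last actual dose of the ABBVIE REGIMEN". EoT response, breakthrough and relapse are widened in the same way. The revision history for version 2.0 records that "the definitions for effectiveness outcomes were adjusted" and gives the reason. Shell Table 2.1.1.1 still labels the primary row "single last HCV RNA value <50 IU/mL 12 weeks after the last actual dose of the ABBVIE REGIMEN", and the EoT row also carries the 50 IU/mL cut alone. Section 15 declares the SAP fully consistent with the protocol.

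**The concern.** The results that SAP 9 newly admits are, on its own account, common. A negative result on a test that cannot detect virus at 50 IU/mL does not show that the load is below 50. Under 9.13.3 such a result is not among those taken as at or below 50; under SAP 9 it is a response. The main SVR12 figure therefore rests on a looser rule than the protocol's analysis section gives.

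Three things stop a reader of the report from seeing this:

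- The output label would describe a 50 IU/mL threshold that was not applied to every patient.
- Section 15 would say that nothing had changed.
- No table in the SAP list gives SVR12 under 9.13.3 or counts the responders whose test had an LLoD above 50 or unknown.

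This matters for the study's purpose. The protocol rationale sets the study against a 60-patient trial with 100% SVR12, where the threshold was 25 IU/mL. Protocol 9.15 says LLoD and LLoQ need documenting so that results can be read against earlier trials. The fields are requested, but no planned table uses them.

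**Working it through.** **Inputs.** Planned size 60 (protocol 9.11; SAP sample size section). Exact two-sided 95% Clopper-Pearson intervals (protocol 9.13.6; SAP 7.2). Cited trial: 60 of 60, 100% (94.0 to 100) (protocol 7.0).

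**Formula.** For x responders of n, the lower limit is the 2.5% quantile of Beta(x, n − x + 1) and the upper limit is the 97.5% quantile of Beta(x + 1, n − x). When x = n, the lower limit is 0.025^(1/n) and the upper is 100%.

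**Documents' own figure.** 0.025^(1/60) = 0.9404, which reproduces the stated 94.0%.

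**Direction.** Every negative result with LLoD at most 50 counts under both rules. A negative result with LLoD above 50 counts under SAP 9 and does not meet 9.13.3. For negative results, then, SAP 9 can add responders but cannot remove any.

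**Size.** Let k be the number of patients whose negative result comes from a test with LLoD above 50. The documents do not give k. The values below are assumptions, not bounds, and take all 60 patients as test-negative. SAP 9 gives 60/60 = 100% (94.0 to 100) for every k.

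| k | 9.13.3, k as failures | 9.13.3, k excluded |
|---|---|---|
| 1 | 59/60 = 98.3% (91.1 to 100.0) | 59/59 = 100% (93.9 to 100) |
| 6 | 54/60 = 90.0% (79.5 to 96.2) | 54/54 = 100% (93.4 to 100) |
| 12 | 48/60 = 80.0% (67.7 to 89.2) | 48/48 = 100% (92.6 to 100) |
| 18 | 42/60 = 70.0% (56.8 to 81.2) | 42/42 = 100% (91.6 to 100) |

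Counted as a failure, each such patient costs 1/60 = 1.67 percentage points. Excluded, the rate stays at 100% and for k = 6 the lower limit falls by 94.0 − 93.4 = 0.6 points.

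**Which column applies.** Section 9.13.3 says when a result is taken as at or below 50, not what to do with other negative results. Section 9.13.1 imputes failure only where a value remains missing, and here a value exists. The protocol settles neither column.

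**The case against.** The strongest reply is that SAP 9 is a reasonable, open adaptation to local testing. Protocol 9.9.1 asks only for an undetectable load, qualitative tests are accepted, and the change and its reason appear in both the revision history and section 9. The protocol is not uniform either: 9.13.3 uses at most 50 where 9.13.4 uses below 50. The study is descriptive, protocol 9.15 already names varying local tests as a limitation, and HCV RNA listings are planned. All of this stands and supports keeping SAP 9 as the main rule. It does not repair the shell labels or section 15, and a listing is not a tabulated result.

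Some stronger readings are tempting but not supported:

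- *Some patients have no place in the core population with sufficient follow-up (CPSFU).* Criteria 2 and 3 in SAP 6 do use the 50 IU/mL cut alone. The text after them, however, excludes only patients with virological response at the last measurement whose SVR12 value is missing for reasons unrelated to safety or effectiveness. Read with SAP 9, that places a patient whose last result is negative. Figure 6.1 is not shown. What remains is a wording mismatch, in a population that is not the protocol's primary one.
- *SAP 3.2 contradicts SAP 9.* Its footnote says the section is based on the protocol's own sections; it restates them.
- *Every detectable but unquantifiable result is ambiguous in SAP 9.* Protocol 9.8.1 keeps positive and negative for qualitative tests. A quantitative result below an LLoQ of at most 50 is therefore below 50 under both rules. Only an LLoQ above 50 stays open in the readable text (Figure 9.1 is not shown). The half-LLoQ substitution in SAP 7.1 sits under descriptive statistics, and nothing says it governs response classification.

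**Conclusion.** The point holds. SAP 9 drops the LLoD condition of protocol 9.13.3 for SVR12 and EoT response, the shell labels and section 15 do not reflect this, and no planned table shows the result under the protocol rule. For negative results the direction is certain: the rates rise or stay the same. The size is unknown, because the documents say only that high limits are frequent.

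In the scenario with 6 of 60 patients affected, the difference is 10 percentage points if they count as failures and none in the rate if they are excluded. A reader might infer from the failure column that the planned analysis inflates SVR12 by 10 points or more. The documents support neither that number of patients nor that handling. Nor do they suggest concealment, since the change is logged with its reason. This should be fixed, but it does not invalidate the main analysis.

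**What to change.** 1. Keep the SAP 9 definitions as the main rule.
2. For the core population, add one sensitivity result for SVR12 and EoT response under 9.13.3. Show negatives with LLoD above 50 or unknown once as failures and once excluded.
3. Tabulate responders by LLoD: at most 50, above 50, unknown.
4. Correct the shell row labels to the rule actually applied, and align the SAP 6 CPSFU wording with SAP 9.
5. List the departure from 9.13.3 in section 15 in place of the statement of full consistency.
6. State how a detectable result below an LLoQ above 50 is classified.

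**Cost.** The LLoD and LLoQ fields are already requested under protocol 9.8.1, so no new data collection is needed. The work is a derived flag, a few extra rows and some text corrections; the EoT result also has to carry the protocol's backward imputation. The sensitivity figure may be less favourable than the main one. Because only available data are collected, the unknown-LLoD line could be large, which would itself be informative.

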9.0 Research Methods

9.1 Study Design

This is a prospective, multi-center observational study in patients receiving the interferon-free ABBVIE REGIMEN without RBV. The prescription of a treatment regimen is at the discretion of the physician in accordance with local clinical practice and label, is made independently from this observational study and precedes the decision to offer a patient the opportunity to participate in this study.

Adult patients chronically infected with HCV and compensated liver cirrhosis, receiving the interferon-free ABBVIE REGIMEN will be offered to participate in this study during a routine clinical visit at the participating sites.

After written Authorization (Consent) for Use/Disclosure of Data form has been obtained, patient data including demographic data, HCV disease characteristics, co-morbidities, co-medication, treatment details, and laboratory assessments as recorded in the patient's medical records (source documentation) will be documented in the electronic case report form (eCRF). Patients will be observed for the duration of the ABBVIE REGIMEN therapy and for up to 12 weeks after treatment completion. No patient identifiable information will be captured, a unique patient number will be automatically allocated by the web based eCRF system once the investigator or designee creates a new patient file.

This study is focusing on collecting real-world data. Follow-up visits, treatment, procedures and diagnostic methods will follow physicians' routine clinical practice.

12-week routine treatment regimen will include at least two observational visits (Visit 1 and EoT) plus one 30 days safety follow-up visit and one 12 weeks follow-up visit (SVR12) after the last dose of ABBVIE REGIMENT. Additional observational visits between Visit 1 and EoT can be done in case of clinical necessity and physician decision.

9.2**Product Supply**

As this is a post-marketing observational study, AbbVie is NOT involved in the product supply since the drug is being used according to the approved market label and is to be prescribed by the physician under usual, current medical practice and is clearly separated from the decision to include the patient in the study.

9.3**Setting**

For the purpose of this program participants will be recruited and observed in approximately 5-7 national and regional hospitals/outpatient services.

9.4**Program Duration**

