4.3 Planned analyses

The only final statistical analysis report will be performed for this study.

No analyses for DMC meetings and no interim analysis are planned in the study.

5 General considerations

Study Day will be calculated from the reference start date, and will be used to show start/stop day of assessments and events.

Reference start date is defined as the day of the start treatment (“EXSTDTC” variable from “EX” domain of the database).

If the date of the event is on or after the reference date then

study day = (date of event – reference date) + 1.

If the date of the event is prior to the reference date then

study day = (date of event – reference date) – 1.

Baseline is defined as the measurement taken on Visit 1.

6 Analysis populations

The target population (TP) – all patients with signed written Patient Authorization, who fulfill the eligibility criteria. Patients who prematurely discontinue earlier than ≤study day 55 will be used in analyses on the target population with actual EoT time point without windowing conventions adjustment for EoT.

The core population (CP) – all patients of the TP, who have started and received the treatment combination recommended in the current local label for their disease characteristics. Patients with EoT ≤ study day 55 (less than 8 weeks) will be excluded from the CP (these patients will be included to the NCP).

The safety population (SP) – all patients who received at least one dose of the ABBVIE REGIMEN.

The non-core population (NCP) – patients not receiving the treatment recommended in the local label.

The core population with sufficient follow-up data (CPSFU) – all CP patients, who fulfill one of the following criteria:

- evaluable HCV RNA data within the SVR12 time window;

¹ This section is based on the section 9.1.1 “Study Size” of clinical study Protocol.

P16-253 (CITRIN) _ STATISTICAL ANALYSIS PLAN _ FINAL 2.0 _ 16 Mar 2018

- a HCV RNA value ≥ 50 IU/mL at the last measurement post-baseline (i.e. no virological response achieved at the last measurement on-treatment or post-treatment);
- HCV RNA <50 IU/mL at the last measurement post-baseline, but no HCV RNA measurement on the SVR12 visit due to reasons related to safety (e.g. dropped out due to AE) or incomplete efficacy information (e.g. virologic failure such as relapse is reported in the eCRF but date and value of the corresponding HCV RNA test is missing).

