 - relapse after EoT (HCV RNA value <50 IU/mL or undetectable/negative at EoT or at the last on-treatment HCV RNA measurement followed by HCV RNA \geq 50 IU/mL or positive post-treatment);
 - failure to suppress (each measured on-treatment HCV RNA value \geq 50 IU/mL or positive);
 - premature study drug discontinuation with no on-treatment virologic failure;
 - missing SVR12 data and/or none of the above criteria.

Figure 9.1 illustrates the patient's distribution by SVR12 response/non-response categories.

P16-253 (CITRIN) _ STATISTICAL ANALYSIS PLAN _ FINAL 2.0 _ 16 Mar 2018

[figure not shown]

Figure 9.1 – Patient's distribution by SVR12 response/non-response categories. Frequencies and percentages with 95% confidence intervals will be calculated for each effectiveness outcomes and will be presented according the section 7.1. Also frequency tables will be repeated for patients in subgroup without missing SVR12 data category.

Effectiveness endpoints (SVR12 achieving, virological response at EoT and relapse after EoT) will be analyzed using univariate logistic regression, if applicable. These analyses will be of exploratory nature, data driven, and will be repeatedly performed for various CP analysis groups, since not each covariate might be predictive in each patient group.

The following parameters can be included in the univariate models as explanatory variables (fixed effect or covariate):

- treatment experience (with/without prior treatment for CHC);
- Child Pugh score;
- result of FibroTest;
- history of liver decompensation;
- age;
- gender;
- race;
- BMI;
- laboratory hematology¹:
 - hemoglobin;
 - platelets;
 - prothrombin time;
 - laboratory clinical chemistry:
 - ALT;

¹ Note that all Hematology variables and all Clinical Chemistry should be in the same units. If it is impossible to bring units to the same the smallest units groups will be accepted as missing. If it is impossible to identify the smallest units groups the corresponding covariate will be deleted from the analysis.

P16-253 (CITRIN) _ STATISTICAL ANALYSIS PLAN _ FINAL 2.0 _ 16 Mar 2018

- AST;
- Gamma-GT;
- total bilirubin;
- albumin;
- creatinine clearance;
- alpha-1-fetoprotein.

Additionally, after univariate model analyses all effectiveness endpoints can be analyzed using MLR (if applicable) which consider only covariates in the selection procedure with a p-value <0.25 in the corresponding univariate logistic regression analysis¹.

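### Failure to suppress has no minimum exposure or sampling time, so an early stop for an adverse event with only an early positive HCV RNA sample is reported as virological failure

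*SAP*

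**What the plan says.** SAP section 9 lists the reasons for not reaching SVR12. One begins "failure to suppress (each measured on-treatment HCV RNA value" and is completed by the threshold alone (50 IU/mL or above, or a positive result). The shell for Table 2.1.1.1 repeats the rule, "Failure to suppress (each measured on-treatment HCV RNA value", again with no duration, sampling day or number of samples.

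The next category in section 9 is "premature study drug discontinuation with no on-treatment virologic failure". The shell spells out what that excludes: "Patients with premature study drug discontinuation with no on-treatment virological failure (breakthrough or failure to suppress". Failure to suppress thus counts as on-treatment virological failure and bars the patient from the discontinuation row.

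On populations, section 9 states: "All analyses of effectiveness will be performed on the TP, CP and CPSFU populations with separate tables for each population as the result". SAP section 6 keeps early stoppers in the target population (TP): "Patients who prematurely discontinue earlier than ≤study day 55 will be used in analyses on the target population with actual EoT time point". Patients with end of treatment (EoT) on or before study day 55 "will be excluded from the CP (these patients will be included to the NCP"; they are therefore also outside the core population with sufficient follow-up (CPSFU).

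On sampling, Protocol section 9.1 says "Additional observational visits between Visit 1 and EoT can be done in case of clinical necessity and physician decision". Protocol section 9.13.1 leaves all HCV RNA testing to the physician. The non-response categories in Protocol section 9.13.5 do not include failure to suppress; the SAP revision history shows it was added in version 2.0.

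**The concern.** The breakdown exists to tell a reader why SVR12 was missed: the regimen did not control the virus, the patient could not stay on it, or follow-up was incomplete. A positive result soon after the first dose says little about whether the virus would have been suppressed by the end of the course. The definition nevertheless treats such a value, when nothing contradicts it, as proof of non-suppression.

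Two patients who stop for the same adverse event at the same time can land in different rows solely because one happened to be sampled early. With few non-responders expected, one such patient could be the whole of the failure-to-suppress row, and the tolerability row would be short by the same patient.

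**Working it through.** **Step 1: apply the wording to example patients.** All four are without SVR12, and none has a post-treatment value.

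| Patient | On-treatment HCV RNA | Row under the text and shell |
|---|---|---|
| A: stops for an adverse event | one early positive | failure to suppress |
| B: stops for an adverse event | none | premature discontinuation |
| C: stops for an adverse event | early positive, then below 50 IU/mL | premature discontinuation |
| D: no premature stop | one early positive, nothing later | failure to suppress (may also meet the missing-SVR12 wording) |

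A and B differ only in whether an early sample was taken. A and C differ only in whether a second sample was taken in time to show suppression.

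**Step 2: find which tables are affected.**
- Patient A with EoT on or before day 55: TP tables only, because SAP section 6 removes this patient from the core population (CP) and hence from CPSFU.
- Patient A with EoT on day 56 or later, or patient D: TP and CP, and also CPSFU, because the last post-baseline value is at least 50 IU/mL (second CPSFU criterion).

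**Step 3: size.** The plan gives no figure for this row, so there is none to reproduce. The inputs are N = 60 (Protocol section 9.11) and two-sided 95% Clopper-Pearson intervals (SAP section 7.2). As a check of the method, 60/60 has lower limit 0.025^(1/60) = 94.0%, which matches the 94.0 to 100% that the protocol cites for the earlier 60-patient trial.

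For x patients in the row, the limits are the 2.5% quantile of Beta(x, 60 − x + 1) and the 97.5% quantile of Beta(x + 1, 60 − x). For x = 0 the upper limit is 1 − 0.025^(1/60) = 5.96%. For x = 1 the lower limit is 1 − 0.975^(1/60) = 0.04%.

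| Patients filed this way (assumed) | Failure-to-suppress row, % (95% CI) |
|---|---|
| 0/60 | 0 (0 to 5.96) |
| 1/60 | 1.7 (0.04 to 8.94) |
| 2/60 | 3.3 (0.41 to 11.53) |
| 3/60 | 5.0 (1.04 to 13.92) |

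Each refiled patient moves the row by 1/60 = 1.7 percentage points.

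**Step 4: what does not move.** These patients are non-responders in whichever row they sit, and Protocol section 9.13.1 counts a value that is still missing as failure. The SVR12 percentage over all patients, its interval, the EoT response and the relapse rate are the same under either filing.

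**The case against.** The strongest reply is that the effect is small and mostly outside the primary population. An early stop is not in CP, which Protocol section 9.13.3 makes the primary effectiveness population. EoT is one of the minimum visits, HCV RNA is listed for it, and early stoppers are asked to return so that EoT data can be documented. The problem therefore needs an early positive and no later on-treatment value below 50 IU/mL. Stopping reasons are tabulated in Table 3.1, and HCV RNA and exposure are listed, so such a patient can be traced. Figure 9.1, which illustrates the allocation, is not shown in the text available and may contain an order or condition. All of this limits the size. None of it changes the written rule, and neither the text nor the shells supply the missing condition.

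A further reply is that the second CPSFU criterion also accepts a last value of 50 IU/mL or above with no minimum time. That is so, but it decides who has enough data to be analysed. It does not assign a reason for non-response.

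A reader might infer more than the documents support:
- *That these patients drop out of the missing-SVR12 category and stay in the tables that omit it.* This is not established. Section 9 reports at least one and each of the categories and joins the missing category with and/or, so overlap is possible. Only the discontinuation row carries an explicit exclusion.
- *That a patient with no on-treatment sample qualifies.* This is strained, because the wording presupposes a measured value.
- *That many patients will have a single early value.* The visit schedule does not support this.

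**Conclusion.** The point holds as a defect in one descriptive category. The stated rule puts an adverse-event stop with only early positive samples in the wrong row. For stops on or before day 55 the effect is confined to the TP tables. CP and CPSFU are reached only through patients with EoT on day 56 or later whose on-treatment samples are all early positives.

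The size is 1.7 percentage points of the row per patient at N = 60. The number of such patients is unknown; 0 to 3 is an assumption for illustration. It would be wrong to read this as bias in the primary result, since the full-denominator SVR12 rate does not change. The conclusion rests on the text and shells, and would need revisiting if Figure 9.1 sets a further condition or order.

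**What to change.** In SAP section 9 and the matching shells, define failure to suppress as follows: at least one on-treatment HCV RNA value exists; all such values are 50 IU/mL or above, or positive; and one of these two conditions holds:
- a minimum exposure and sampling time, stated in advance, is met, for example the SAP's own 8-week cut with the last sample in the EoT window;
- the recorded reason for stopping is virological non-response, breakthrough or resistance.

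File other early stoppers under premature discontinuation. State in the text, and not only in a figure, whether the categories are mutually exclusive and in what order they apply, including against missing SVR12 data.

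The cost is a few lines of SAP text and one derivation. The dates and stopping reasons it needs are already planned for collection (Table 3.1 lists the reasons). SAP section 2 allows revision before database soft lock; after that, the change would be explained in the study report. The small downside is that a true early non-responder with no recorded reason for stopping would appear as a discontinuation.
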